1 SUMMARY

PS0017 is a randomized, double-blind, parallel group, placebo (PBO)-controlled, multicenter study designed to evaluate the efficacy and safety of certolizumab pegol (CZP) in adult Japanese subjects with moderate to severe chronic plaque psoriasis (PSO). In addition, a cohort of subjects with generalized pustular PSO or erythrodermic PSO will be eligible for the study.

Approximately 125 subjects with moderate to severe chronic plaque PSO, including psoriatic arthritis (PsA), will be randomly assigned in a 2:2:1 ratio at Baseline to either CZP 400mg every 2 weeks (Q2W), CZP 200mg Q2W (loading dose of CZP 400mg at Weeks 0, 2, and 4), or PBO. Study drug will be administered by subcutaneous (sc) injection. Subjects will be followed in a blinded fashion up to Week 52 following randomization.

The treatment from Week 16 through Week 52 for subjects who achieve a Psoriasis Activity and Severity Index (PASI) 50 response will be based on response to double-blind treatment at Week 16. Subjects randomized to CZP 400mg Q2W will remain on their assigned dose. Subjects initially randomized to CZP 200mg Q2W will be rerandomized (1:1) to receive either CZP 200mg Q2W or CZP 400mg Q4W (with PBO administered on alternate dosing weeks to maintain the blind). Subjects randomized to PBO treatment who achieve a PASI50 response at Week 16 will continue on PBO. Subjects who do not achieve a PASI50 response at Week 16 will escape from double-blind treatment and enter the open-label arm of the study.

Subjects who do not achieve a PASI50 response at the Week 16, 24, 32, or 40 visit will escape from double-blind treatment and enter the open-label arm of the study. These subjects will receive open-label CZP (400mg Q2W as 3 loading doses followed by CZP 200mg Q2W) from the visit the response criterion is not met. Subjects receiving open-label CZP 200mg Q2W in the escape arm and not achieving a PASI50 response will be allowed to have their dose increased to CZP 400mg Q2W, at the discretion of the Investigator. If, in the opinion of the Investigator, the subject is not receiving benefit (eg, a PASI50) at the 400mg Q2W dose, the subject should be withdrawn from the study.

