5.1.1 Study design for subjects with moderate to severe chronic plaque PSO

5.1.1.1 Period 1: Screening

The Screening Period of 2 to 5 weeks will be used to confirm eligibility; obtain laboratory data; verify that the doses of nonsteroidal anti-inflammatory drugs (NSAIDs) and other pain relievers, such as acetaminophen, paracetamol, or mild opiates, if used to treat PsA are stable; and enable washout of any medications not permitted for use during the study.

5.1.1.2 Period 2: Week 0 to Week 16

Eligible subjects will be allocated to the following study treatments in a 2:2:1 ratio:

- CZP 400mg (n=50): CZP administered sc at the dose of CZP 400mg Q2W
- CZP 200mg (n=50): CZP administered sc at the dose of CZP 400mg at Weeks 0, 2, and 4, followed by CZP 200mg Q2W (starting at Week 6)
- PBO (n=25): PBO administered sc Q2W

Study treatments (including PBO) will be administered by dedicated, unblinded, trained site personnel at Baseline and Q2W thereafter to Week 16.

5.1.1.3 Period 3: Week 16 to Week 52

The treatment received in Period 3 will be based on response to double-blind treatment at Week 16. All CZP and PBO treatments will be administered by dedicated unblinded site personnel at site visits, excluding the escape treatment.

Subjects who achieve a PASI50 response at Week 16 will continue therapy as follows:

- Subjects initially randomized to CZP 400mg Q2W will continue to receive CZP 400mg Q2W.
- Subjects initially randomized to CZP 200mg Q2W will be re-randomized (1:1) to receive either CZP 200mg Q2W or CZP 400mg Q4W (with PBO administered on alternate dosing weeks to maintain the blind).
- Subjects initially randomized to PBO will be continue to receive PBO.
- Subjects who do not achieve a PASI50 response at Week 16, 24, 32, or 40 will escape from double-blind treatment and receive open-label CZP treatment (400mg Q2W as 3 loading doses followed by CZP 200mg Q2W) from the visit the response criterion is not met. Subjects receiving open-label CZP 200mg Q2W in the escape arm and not achieving a PASI50 response will be allowed to have their dose increased to CZP 400mg Q2W at the visit the criterion is not met, at the discretion of the Investigator. If, in the opinion of the Investigator, the subject is not receiving benefit (eg, a PASI50) at the 400mg Q2W dose, the subject should be withdrawn from the study.

Subjects who do not achieve a PASI50 response at Week 16 will escape from double-blind treatment and receive treatment as follows:

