2.3.1 Study design for subjects with moderate to severe chronic plaque PSO

2.3.1.1 Period 1: Screening

The Screening Period of 2 to 5 weeks will be used to confirm eligibility; obtain laboratory data; verify that the doses of nonsteroidal anti-inflammatory drugs (NSAIDs) and other pain relievers, such as acetaminophen, paracetamol, or mild opiates, if used to treat PsA are stable; and enable washout of any medications not permitted for use during the study.

2.3.1.2 Period 2: Initial Period - Week 0 to Week 16

Eligible subjects will be allocated to the following study treatments in a 2:2:1 ratio:

- CZP 400mg Q2W (n=50): CZP administered sc at the dose of CZP 400mg Q2W

- CZP 200mg Q2W (n=50): CZP administered sc at the dose of CZP 400mg at Weeks 0, 2, and 4, followed by CZP 200mg Q2W (starting at Week 6)
- PBO (n=25): PBO administered sc Q2W

Study treatments (including PBO) will be administered by dedicated, unblinded, trained site personnel at Baseline and Q2W thereafter to Week 14. Week 16 is the last study visit during this period.

2.3.1.3 Period 3: Maintenance Period - Week 16 to Week 52

The treatment received in Period 3 will be based on response to double-blind treatment at Week 16. All CZP and PBO treatments will be administered by dedicated, unblinded, trained site personnel at site visits, excluding the escape treatment.

Subjects who achieve a PASI50 response at Week 16 will continue therapy as follows:

- Subjects initially randomized to CZP 400mg Q2W will continue to receive CZP 400mg Q2W.
- Subjects initially randomized to CZP 200mg Q2W will be re-randomized (1:1) to receive either CZP 200mg Q2W or CZP 400mg Q4W (with PBO administered on alternate dosing weeks to maintain the blind).
- Subjects initially randomized to PBO will continue to receive PBO.

Subjects who do not achieve a PASI50 response at Week 16, 24, 32, or 40 will escape from double-blind treatment and receive treatment as follows:

- Escape treatment: Subjects entering the escape arm of the study will receive open-label CZP treatment (400mg Q2W as 3 loading doses followed by CZP 200mg Q2W). Subjects receiving open-label CZP 200mg Q2W in the escape arm and not achieving a PASI50 response will be allowed to have their dose increased to CZP 400mg Q2W, at the discretion of the Investigator. If, in the opinion of the Investigator, the subject is not receiving benefit (eg, a PASI50) at the CZP 400mg Q2W dose, the subject should be withdrawn from the study.

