4.2 Handling of dropouts or missing data

PASI 75/50/90/100 and PGA:

- Initial Period

Missing data for the primary variable and other key efficacy variables (eg, PASI50, PASI90, PASI100, and PGA) will be handled using the Markov Chain Monte Carlo (MCMC) method for multiple imputation. Sensitivity analyses which apply different methods of handling missing data for the primary endpoint are planned. Further details are provided in Section 8.1.3.

- Maintenance Period

Subjects can switch to the CZP 200mg Escape Arm (400mg Q2W as 3 loading doses followed by CZP 200mg Q2W) due to lack of PASI50 response at multiple time points (at Week 16 or later). They are treated as non-responders from the time of escape onwards for by

blinded maintenance group tables. Observed PASI50 responses after escape are only relevant for Escape Arm outputs. Other missing data will be handled using the MCMC method for multiple imputation.

Missing data after escape because of discontinuation after escape will be imputed accordingly.

For the cohort missing data will be imputed accordingly, and summaries will be based on MCMC imputed data and on observed case data over time.

Other Binary Efficacy Variables:

- Initial Period

Other binary efficacy variables that are summarized without statistical modeling will use non-response imputation (NRI) as the method for handling missing data. Non-responder imputation (NRI) is a method for dichotomous (“yes (1) or no (0)”) or categorical variables, where a subject is considered a non-responder if certain criteria are met. Typically, if a subject drops out of a study, that subject is analyzed as a non-responder, regardless of whether or not the subject was responding to treatment at the time of dropout.

- Maintenance Period

Other binary efficacy variables that are summarized without statistical modeling will use NRI as the method for handling missing data. Escapers will be treated as non-responders from the time of escape onwards for by blinded maintenance group tables. Observed data after escape is only relevant for Escape Arm outputs.

Missing data after escape because of discontinuation after escape will be imputed accordingly.

For the cohort missing data will be imputed, and summaries will be based on NRI imputed data and on observed case data over time.

Continuous Variables:

- Initial Period

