PASI50, PASI75, PASI90 and PASI100 responder rates (based on simple counts and percentages only) will be also summarized for the Blinded Maintenance Period (Week 16 through Week 24) by blinded maintenance treatment group (combined group inclusive) using NRI imputed and observed data.

A table summarizing the (exact) logistic regression analysis results of PASI75/PASI90 response rates during Blinded Maintenance Period based on the subset of PASI75/PASI90 responders at Week 16 will also be provided (observed case, NRI and MCMC imputed data), procedure as outlined in [Section 8.1.2](#). Additionally, the same table will be produced to summarize simple counts and percentages using the blinded maintenance treatment groups (combined group inclusive) based on NRI and observed data only.

Line plots will be generated to present the percentages of responders over time by blinded maintenance treatment group (Blinded Maintenance Period treatment) over time (from Week 16 to Week 24) based on MCMC imputed data.

Maintenance Period (Final Analysis, including subjects who escaped after Week 16)

The analysis of the PASI50, PASI75, PASI90, and PASI100 responder rate during the Maintenance Period will be based on the BM FAS. Missing data will be handled based on a combination of NRI and multiple imputation. The procedure is described below:

1. Identify subjects who met the escape criterion at any timepoint (ie, did not achieve a PASI50 response), and do not include them in the multiple imputation model described in Step 2.
2. For all subjects not identified in Step 1, create a data set, one for each treatment group, of subjects with observed values and those needing estimation by multiple imputation. The missing PASI values in each data set will be filled in using the MCMC method with a total of 75 sets of imputations being performed. The procedure will sequentially estimate an imputation model for the PASI score at each post-Baseline visit where PASI is collected, with prior biologic exposure and Baseline score as predictors. The resulting data sets for each treatment arm will be combined into one complete data set based on each of the 75 imputations.

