3. For the subjects meeting the escape criterion identified in Step 1, all visits after the point of escape will be imputed via NRI. This imputation is based on meeting the escape criterion, whether or not the subject actually received escape treatment. Once imputation has been performed for these subjects, these records are duplicated 75 times and combined with the 75 imputations performed in Step 2.

Note: If subjects identified here have intermittent missing data at earlier time points, those will be imputed via NRI.

4. For each complete imputed data set, the dichotomous PASI responder rate based on the PASI scores will be computed. Each complete imputed data set will then be analyzed using simple proportions by treatment group ($p=x/N$, where x is the number of responder and N the number of subjects in this treatment group). The corresponding standard error for the sample proportion will be calculated with the square root of $p(1-p)/N$.

Note: For derivation of PASI75 response, the imputed PASI value will be compared directly to the observed Baseline PASI value to determine whether or not a reduction of at least 50% (or 75%, 90%, 100%) was achieved. If values outside of the pre-defined range

of values for PASI (0-72) are imputed, they will be cut off as appropriate after the multiple imputation procedure but before deriving the responder variables. For example, an imputed PASI value of -0.5 would be changed to 0 before deriving the PASI responder variable.

5. The results at each week of each of the 75 imputed data sets will be combined into a single inference using SAS PROC MIANALYZE.

The estimated responder rates at each week will be presented by treatment group based on the FAS.

Additionally, NRI will be used for imputation of missing data. Simple proportions will be calculated to estimate responder rates at each visit in the Maintenance Period (ie, Week 16 through Week 52). Responder rates based on observed case data will also be summarized.

A table summarizing the PASI75/PASI90 response rates (simple proportions) during Maintenance Period based on the subset of PASI75/PASI90 responders at Week 16 will also be provided (observed case, NRI and MCMC imputed data).

Line plots will be generated to present the percentages of responders over time by maintenance treatment group over time (from Week 16 to Week 52) based on MCMC imputed data.

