8.3.4 PGA score distribution

See Section 8.2.1 for details of the derivation. The summaries described in this section are based on observed data – no imputation will be performed.

Initial Period

The distribution of the PGA score (0, 1, 2, 3, or 4) will be summarized in shift tables comparing the change from Baseline versus post-Baseline (Weeks 2, 4, 8, 12 and 16) by randomized treatment group for the FAS and EPS. The shift tables will be provided for each time point.

Maintenance Period

The distribution of the PGA Score will be summarized in shift tables comparing the change from Baseline versus post-Baseline (Weeks 16, 20, 24, 28, 32, 36, 40, 44, 48 and 52) by blinded maintenance or escape maintenance treatment group for the FAS and by maintenance treatment group for EPS. The shift tables will be provided for each time point.

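### SAP 8.3.1, final maintenance analysis: as worded, one PASI50 miss at a visit where escape is not decided turns later observed blinded responses into non-responses

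*SAP*

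**What the plan says.** **When escape is decided.** Protocol 5.1.1.3: "Subjects who do not achieve a PASI50 response at Week 16, 24, 32, or 40 will escape from double-blind treatment". SAP 2.3.1.3 names the same four visits: "Subjects who do not achieve a PASI50 response at Week 16, 24, 32, or 40 will escape".

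**When response is measured.** SAP 8.3.4 lists the maintenance visits for PGA as "Weeks 16, 20, 24, 28, 32, 36, 40, 44, 48 and 52". Protocol section 8 schedules PASI at the same weeks. After Week 16 and before Week 52, the visits with a PASI score but no escape decision are therefore Weeks 20, 28, 36, 44 and 48.

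**The final maintenance analysis (SAP 8.3.1).** Step 1: "Identify subjects who met the escape criterion at any timepoint (ie, did not achieve a PASI50 response"; these subjects are left out of the multiple imputation model. Step 3: for them, "all visits after the point of escape will be imputed via NRI", with the explanation "This imputation is based on meeting the escape criterion, whether or not the subject actually received escape treatment". SAP 8.3.2 uses the same method for PGA response.

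**Elsewhere in the SAP.** Section 4.2 says of subjects who switch to the escape arm: "They are treated as non-responders from the time of escape onwards". Section 3.5.9 bases the final Blinded Maintenance analyses on the data observed under blinded treatment, with imputation after escape. In the final combined-period NRI table of 8.3.1, a subject who does not escape becomes a non-responder only on premature withdrawal.

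**The concern.** Step 1 reduces the escape criterion to lack of PASI50 response and attaches no visit to it, and Step 3 separates the imputation from actual escape. Together they reach a subject the protocol never meant to move: one who dips below PASI50 at, say, Week 20, is above it again at Week 24, and correctly stays on blinded drug. That subject's valid later observations would be replaced by failure for PASI50, 75, 90 and 100 and for PGA, and the same subject would appear as a responder in other tables of the same report.

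Durability of response under maintenance treatment is a stated secondary objective, and SAP 4.3 gives its assessment as a purpose of the final analysis. The affected rates are the ones plotted from Week 16 to Week 52.

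**Working it through.** **1. One subject under each rule.** Take a subject with PASI50 at Week 16, a miss at Week 20, PASI50 at every visit from Week 24 to Week 52, no escape and no withdrawal.

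| Rule | Status at Weeks 24 to 52 |
|---|---|
| SAP 8.3.1 Steps 1 and 3, read literally | Non-responder |
| SAP 8.3.1 Steps 1 and 3, criterion confined to Weeks 16, 24, 32, 40 | As observed |
| SAP 4.2 | As observed |
| SAP 3.5.9, final analysis | As observed |
| SAP 8.3.1, combined-period NRI | As observed |
| SAP 8.3.1, observed-case summary | As observed |

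Only the literal reading of Steps 1 and 3 departs from the rest.

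**2. Is the literal reading credible?** In the interim part of 8.3.1, and again in 8.3.2, the criterion for escape is glossed as not achieving PASI50, and the visit (Week 16) is named separately. Step 1 uses the same gloss and puts any timepoint where the visit would stand.

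**3. Size.** The plan gives no figure for this rule and no PASI variability, so every input in this step is an assumption.

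*Chance of a flag.* With an assumed miss rate q at each of the five non-decision visits, independent between visits, a subject who passes every decision visit is flagged with probability 1 − (1 − q)^5:

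| q | P(flag) | Expected number in an arm of 25 |
|---|---|---|
| 1% | 4.9% | 1.2 |
| 2% | 9.6% | 2.4 |
| 5% | 22.6% | 5.7 |
| 10% | 41.0% | 10.2 |

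This overstates the effect if misses cluster in the same subjects, so a model with within-subject correlation is the better guide.

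*Correlated model.* Percentage PASI improvement equals a normal subject mean plus independent normal visit noise, capped at 100. There are 400,000 simulated subjects per row, and the denominator is Week 16 PASI50 responders. A Week 52 response counts only if the subject was not flagged earlier, first under the decision-visit rule and then under the any-visit rule.

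| Mean / between-subject SD / visit SD | Passes decision visits but flagged | Week 52 PASI50, decision-visit | Week 52 PASI50, any-visit | PASI50 loss (points) | PASI75 loss (points) |
|---|---|---|---|---|---|
| 85 / 15 / 5 | 1.0% | 98.4% | 97.6% | 0.8 | 0.0 |
| 85 / 15 / 10 | 3.9% | 94.7% | 91.2% | 3.5 | 0.8 |
| 80 / 20 / 10 | 6.3% | 88.7% | 83.3% | 5.5 | 0.9 |
| 75 / 20 / 10 | 8.1% | 84.9% | 78.0% | 6.9 | 1.1 |

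*All randomised subjects as denominator.* SAP 3.5.9 and 3.6.1 keep Week 16 escapers in the final tables. Assume a mean of 75 to 82 (SD 18 to 20) on CZP, a mean of 35 (SD 30) on placebo, and a visit SD of 5, 8 or 12. The Week 52 PASI50 loss is then about 1.5 to 7 points on CZP and 2 to 4 on placebo. The PASI75 loss is at most about 2 points on CZP and 0.8 on placebo.

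*Granularity.* Of the 50 subjects planned for CZP 200mg Q2W, the Week 16 PASI50 responders are re-randomised 1:1, so each arm gets at most about 25. One overwritten subject moves such a rate by at least 100/25 = 4 points. (The CZP 200mg Q2W/200mg Q2W row also takes in that group's Week 16 escapers, so its denominator can be larger; the CZP 400mg Q4W row's cannot.)

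**The case against.** The best defence is that the escape criterion means the protocol's rule, which exists only at Weeks 16, 24, 32 and 40. Any timepoint would then mean any of those visits, in contrast to the interim analysis, which deals only with escape at Week 16. The clause about not receiving escape treatment would cover a subject who failed at a decision visit but was not switched. Two points support this. Taken fully literally, Step 1 would also catch Weeks 2 to 12, when many subjects have not yet reached PASI50, so some limit must have been intended. And a point of escape has no meaning at Week 20. On this reading nothing is overwritten.

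That defence stands as a possible reading, so a reader should not infer that the plan has settled on overwriting blinded data. It does not remove the problem. The limit is nowhere in Steps 1 or 3, the same section elsewhere separates criterion from visit, and the point of escape is undefined for a subject who met the rule but was not switched.

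Two other inferences go too far:

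- **That PBO/PBO suffers most.** Among subjects who pass every decision visit, placebo responders sit nearer the PASI50 line, and their assumed overwriting rate is higher. But the reported rate divides by a group that includes Week 16 escapers. On that denominator CZP loses more points than placebo at visit SDs of 8 and 12, while at an SD of 5 one CZP scenario loses less (1.5 against 2.0). The order depends on the assumptions.
- **That the whole maintenance analysis is biased.** The observed-case summary and the combined-period NRI table are untouched, and the separate NRI summary is described as imputing missing data.

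**Conclusion.** The concern holds as a defect of wording with a real consequence. Followed as written, Steps 1 and 3 convert observed responses to non-responses in subjects correctly kept on blinded treatment, and they contradict SAP 3.5.9, 4.2 and the combined-period NRI rule. If the programmer applies a decision-visit reading, the effect is zero, but the SAP should not leave that choice open.

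The reach is limited to the descriptive MI/NRI maintenance responder rates for PASI and PGA and the MCMC line plots. SAP section 8 confines comparisons of CZP with placebo to the period through Week 16, so the primary endpoint, the alpha allocation and the sample size are unaffected.

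Under the literal reading, a loss of roughly 1 to 7 points in the Week 52 PASI50 rate and about 0 to 2 points in PASI75 is plausible. Those ranges are illustrations: the means, the SDs and the independent visit noise are all assumed. No claim is made about which arm is most affected.

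**What to change.** - **Step 1:** replace the any-timepoint wording with *at a decision visit (Week 16, 24, 32 or 40)*.
- **Step 3:** define the point of escape as the first decision visit at which PASI50 was not achieved, and apply NRI after that visit whether or not escape treatment was given.
- **All other subjects on blinded treatment:** keep observed data, with multiple imputation for missing values.
- **SAP 8.3.2:** mirror the change for PGA.

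The whether-or-not clause should stay. Tying NRI only to the start of escape treatment would leave a gap: a subject who failed at Week 24, was not switched and then withdrew would be out of the imputation model under Step 1 and outside NRI under Step 3.

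Cost: a few words in the SAP and a small program change. No new data are needed.
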